1.2. Methodological aspects

medical product of interest Not applicable
First ethics committee to evaluate the study: Autonomous CEIm of Galicia
Principal Investigators / Coordinators [REDACTED] [REDACTED]

[REDACTED]
 
[REDACTED]
 
[REDACTED]

Researcher/Coordinator Centers:
 
¹ Valencian Institute of Oncology
 
² San Carlos Clinical Hospital of Madrid
 
³ Puerta del Hierro-Majadahonda University Hospital
 
⁴ Lucus Augusti University Hospital, Lugo

Autonomous Communities of Researchers / Coordinators:
 
Valencian Community
 
Autonomous Community of Madrid
 
Galicia

Territorial scope:
 
National, Spain

Information source:
 
Medical records of the patients included after signing informed consent.
 
RETROSPECTIVE PART ONLY: medical records of patients included after signing informed consent or waiver thereof in the cases contemplated (see 6.3 Informed consent).

Type of study (according to the AEMPS classification):
 
EPA-AS

Tracking Type::
 
Ambispective (Prospective and retrospective). A 6-month follow-up is proposed for patients in the prospective part.

Total number of patients expected to include:
 
They are expected to include 250, sufficient to respond to the objectives set by the study.

Planned duration of the study:
 
Data collection 8 months. The estimated duration of the project is 12 to 18 months, depending on the patient inclusion rate.

Study duration for each participant:
 
No specific study visits will be carried out, other than obtaining informed consent in cases where it is required.

Main objectives:
 
a) Main objectives
 
i) Describe the population infected by COVID-19 with genitourinary tumors (urothelial cancer, prostate cancer, testicular cancer and renal cancer) treated in Spanish hospitals, know the clinical presentation, therapeutic evolution and

- prognosis of said intercurrent infectious process, as well as its possible relationship with different clinical and therapeutic factors.
- ii) Assess the possible relationship of the different oncological treatments administered to these patients with the clinical evolution of COVID-19 infection, considering both patients who have undergone oncological treatment previously, during or after COVID-19 infection.

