4.3. Inclusion criteria

- Patients ≥18 years old.
- Diagnosed with genitourinary cancer (urothelial, kidney, prostate and germ cell).
- COVID-19 infection prior to oncological treatment, during treatment or after treatment.
- COVID-19 infection must be confirmed by PCR or serology, regardless of whether or not the patient requires hospitalization due to the infection. Additionally, clinical and/or radiological determination must be available in those patients who present symptoms.

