5. VARIABLES

5.1. Study variables

A data collection notebook will be prepared in which the following variables will be collected for analysis:

Affiliation of the center:

- Hospital name
- Province
- Investigator's name
- Patient number

Patient characteristics:

- Age
- Sex
- Age
- Hospital center where the patient is recruited (in order to have epidemiological data on the pandemic that may be of interest)

Pathological history:

- Concomitant pathology (cardiac, pulmonary, renal, liver, Diabetes Mellitus, HIV, AI)
- Usual pharmacological treatment
- Smoking and alcohol habit

Tumor pathology:

- Tumor type, histology and stage (initial and at diagnosis of infection)
- Date of cancer diagnosis
- Active cancer treatment or follow-up
- Participation in clinical trial
- Type of treatment most recently received for the infection (Surgery; Radiotherapy; Chemotherapy: Drug, Immunotherapy, TD: Drug, HT: ADT alone or with Abiraterone, Enzalutamide, others)
- Treatment lines
- Start and last dose received of the most recent oncological treatment

For patients with prostate cancer:

- Local treatment and type (Surgery, Radiotherapy)
- Adjuvant ADT or advanced disease (start date)
- NAH (date and line of treatment)
- Associated corticosteroid treatment: Prednisone vs Dexamethasone (dose)

COVID-19 infection data:

- Confirmation date of COVID-19 infection
- PCR diagnostic test
- IgG or IgM serological diagnostic test
- Present symptoms

- Analytical alterations, lymphopenia, elevated CRP, high D-dimer.
- Thrombosis associated with COVID-19 infection
- Date of onset and disappearance of symptoms
- Days duration of fever and cough
- Radiological examination at the moment of greatest severity
- Complications of infection: presence of complications and/or hospital or ICU admission
- Admission date
- Date of most serious complication
- Treatments received for COVID-19
- Discharge status
- Fecha de alta / exit
- Negativization of the presence of viruses by PCR
- Negative PCR date

For patients who are receiving or have received immunotherapy treatments, additional information will be collected:

- Immunotherapy treatment line
- Start/end date of immunotherapy treatment
- Date of last dose received prior to COVID-19 infection
- Immunotherapy received as monotherapy or combination
- Type of immunotherapy
- Adverse effects

Prospective follow-up data (6 months from patient inclusion):

- Date of start or restart of oncological treatment after infection

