- Negative COVID-19 test prior to starting/restarting treatment
- Change/suspension of oncological treatment after COVID-19
- Surgery date in neoadjuvant patients
- Recurrence of COVID-19
- Best answer obtained
- Date of progression to oncological treatment
- Current status
- Last contact date

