6.3. Informed consent

All information will be extracted from the medical records of participating patients who have authorized its use by signing the informed consent. All patients included in the prospective part of the study, upon authorization by the competent authorities, must sign an informed consent prior to their inclusion in the study that authorizes the use of the information contained in their medical records.

RETROSPECTIVE PART ONLY: In all cases where it is possible for the patient to sign informed consent, it will be collected. Due to the nature of the study and in order not to generate information bias in those patients with a worse prognosis who have not been able to overcome the disease, exemption from informed consent is contemplated for patients who have died in the retrospective part of the study. study, prior to authorization of the study by the competent authorities.

RETROSPECTIVE PART ONLY: The local Ethics Committee must approve the absence of written authorization by signing the informed consent (as established by local Spanish regulations: SAS

Order 3470/2009). It is possible to dispense with the request for informed consent of patients who have died prior to the authorization of this study by the competent authorities provided that a prior refusal has not been obtained for the signing of the informed consent by of the patient or a revocation thereof. On the other hand, this methodology has been proposed taking into account that:

- There are no studies on the involvement of COVID in patients affected by the disease under study
- The high incidence of fatal cases leads to the need to collect these cases in order not to cause bias in the sample due to relevant loss of patients that generates serious problems of representativeness of the population under study and scientific validity.

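### Follow-up is timed from study inclusion, but neither an inclusion date nor a retrospective/prospective flag is listed, so undated outcomes cover unequal times since infection and late entry cannot be adjusted for

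*Combined protocol and SAP*

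**What the plan says.** All references are to the combined protocol and SAP.

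- **Window.** Section 5.1 labels the last group of variables "Prospective follow-up data (6 months from patient inclusion". Section 1.2 limits it to one part of the study: "A 6-month follow-up is proposed for patients in the prospective part".
- **Entry.** In the prospective part patients "must sign an informed consent prior to their inclusion in the study" (section 6.3), and under section 4.8 data collection starts only after consent or an approved waiver. For the retrospective part, section 6.3 says "exemption from informed consent is contemplated for patients who have died in the retrospective part of the study", and limits this to deaths before the study was authorised.
- **Lag.** Section 4.3 places infection only in relation to cancer treatment: "COVID-19 infection prior to oncological treatment, during treatment or after treatment". It sets no maximum time from infection to inclusion.
- **Dates listed in 5.1.** These include "Confirmation date of COVID-19 infection", "Date of onset and disappearance of symptoms", admission, discharge, start or restart of treatment, progression and "Last contact date".
- **Not listed in 5.1.** There is no inclusion date, no consent date and no retrospective/prospective indicator. Recurrence of COVID-19, change or suspension of treatment, and best response have no date of their own.
- **Analysis.** Section 4.5 names Kaplan-Meier curves and the log-rank test, with no time origin, censoring rule or treatment of late entry.

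**The concern.** The questions about the period after infection concern time since COVID-19, but the clock starts at an administrative event. Inclusion depends on when a centre is approved and opened and on when the patient can sign. Two patients with the same course after infection can therefore be observed over different stretches of it, and the difference may follow the centre's opening date more than anything clinical.

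Two results are exposed. Outcomes recorded without a date can only be reported as proportions, and those would pool different lengths of time since infection. Change of treatment is one of them, and it feeds a secondary objective (section 3.2). Second, a consented prospective patient had to be alive at inclusion. If survival is timed from infection and the months before inclusion are counted as time at risk, that group's mortality is understated. Correcting this needs the entry date, which is not among the listed variables.

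**Working it through.** The plan has no figure of its own to reproduce on this point. The expected 250 patients are not calculated and are not in dispute.

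**1. What the listed dates allow.** Last contact minus confirmation gives the time since infection actually observed. Progression minus confirmation, and restart minus confirmation, are also available. Inclusion minus confirmation is not, because inclusion is not listed.

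**2. End of the window after infection** = lag + 6 months. The lags are assumed, since the documents give none:

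| Lag (months) | Window ends, months after infection |
|---|---|
| 0 | 6 |
| 1 | 7 |
| 3 | 9 |
| 6 | 12 |

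As a plausibility check, take infection on 11 March 2020 (the pandemic declaration in section 2.2, used as an assumed early infection date) and inclusion in 3Q 2020 (the study start in section 4.9). From 11 March to 1 July is 112 days, and to 30 September 203 days. Divided by 30.4375, these give lags of 3.7 and 6.7 months, so the window would end 9.7 to 12.7 months after infection.

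**3. Undated outcomes.** Assume a constant risk of 5% per month and records read from infection onward. The proportion with the event is 1 − 0.95^6 = 26% over 6 months and 1 − 0.95^11 = 43% over 11 months (a 5-month lag), from the same underlying risk. If only events after inclusion were counted, each window would be 6 months long but would cover a different period after infection. The plan does not say which is meant. Without event dates, neither version can be brought to a common window afterwards.

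**4. Entry conditional on survival.** Assume true 6-month mortality p, with 80% of deaths spread evenly over month 1 and 20% over months 1 to 6. Assume lags uniform from 0 to M months, and that only patients alive at inclusion enter. The share of deaths falling after inclusion is q:
- M = 3: early deaths 0.5/3 = 0.167; late deaths (1/5)[(9 − 1)/6 + 3] = 0.867; q = 0.8 × 0.167 + 0.2 × 0.867 = 0.307.
- M = 6: early deaths 0.5/6 = 0.083; late deaths 3.5/6 = 0.583; q = 0.8 × 0.083 + 0.2 × 0.583 = 0.183.

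Apparent mortality with no entry adjustment = pq / (pq + 1 − p):

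| True p | M = 3 | M = 6 |
|---|---|---|
| 10% | 3% | 2% |
| 20% | 7% | 4% |
| 30% | 12% | 7% |

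These figures describe a group made up only of consented patients. They show a direction for that group and not an expected size for the study.

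**5. The waiver.** It adds patients who had died before authorisation, which pushes pooled mortality the other way. Patients who die after authorisation and before consent have no stated route in. Patients entering by waiver are all dead and consented prospective patients were all alive at entry, yet no listed variable separates the two routes.

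**6. Completeness.** Extraction ends in 1Q 2021 (section 4.9), at the latest on 31 March 2021. A patient included after 30 September 2020 cannot complete 6 months from inclusion by then. Without the inclusion date, the analyst cannot tell from the listed variables who did.

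**The case against.** The other side has several good points.

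- **Follow-up time can be derived.** A reader might infer that patients' time after infection cannot be reconstructed. The documents do not support that: confirmation and last contact dates are both listed, and Kaplan-Meier censoring deals with unequal follow-up for dated events such as progression. This stands. It does not help the undated outcomes, and censoring deals with when observation ends, not when it begins.
- **No 6-month percentage is planned.** Section 3.2 defines mortality at discharge and otherwise names average delay, number of modifications, time to progression and overall survival. This stands. Discharge status does not depend on the length of the window.
- **Early deaths are not simply lost.** A reader might infer that study mortality must be too low. Section 6.3 brings in deaths before authorisation so as to avoid that bias, and section 4.6 requires consecutive inclusion. This largely stands. The interval from authorisation to consent remains open.
- **Infection is not stated as the survival origin.** True. Dates of cancer diagnosis and treatment are also listed, and comparison with tumour-specific reference values may use those. The omission of an origin is part of the gap.
- **The lag might be recovered.** Sites keep signed consent forms (section 8.2) and database activity is logged (section 6.3). Neither is planned as analysis data, waived patients have no consent form, and a log date is only a proxy for inclusion.
- **The follow-up applies to the prospective part only, and the analysis is described as descriptive.** Both are true and limit the reach of the point. The documents do not say which part a patient infected months before being approached belongs to, so a part indicator is needed.
- **Delayed entry for everyone would do harm.** This stands in full. Waived patients are included after death and would drop out of the risk set, which would undo the purpose of the waiver.

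**Conclusion.** The concern holds in a limited form. The window starts at inclusion, the lag from infection is unlimited, and neither inclusion date nor study part is listed. As a result, recurrence, change or suspension of treatment, and best response would be reported over unequal times since infection, and survival between infection and inclusion of consented prospective patients cannot be accounted for from the listed variables.

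The size is not known. The window ends 6 months after infection plus the lag. The 26% against 43%, and the mortality table, rest on assumed hazards and lags. Waived deaths and conditional survival act in opposite directions, so neither the direction nor the size of the net bias can be stated. The documents do not support a claim that the follow-up is unusable or that mortality is necessarily understated. The change is still worth making: it alters a stated rule at little cost, and entry dates are easier to record during collection than to recover afterwards.

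**What to change.** 1. In sections 5.1 and 1.2, define the follow-up window from the date infection was confirmed. Extract records from that date onward, and keep later data up to last contact.
2. Add dates for COVID-19 recurrence, change or suspension of treatment, and best response, or report these outcomes over a common 6-month window after infection.
3. Add to the eCRF the inclusion date and the patient's status: retrospective or prospective, consented or waived.
4. In section 4.5, state confirmed infection as the time origin for post-infection survival.
5. In those curves, let consented prospective patients enter the risk set at inclusion (delayed entry). Analyse or report the retrospective part, including waived deaths, separately and without delayed entry.

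Delayed entry does not recover deaths between authorisation and consent, so the report should state that these are unobserved.

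Cost: a few eCRF fields and a few sentences of text. No visits are added, because the data come from medical records (section 4.1). Survival intervals in the prospective part will be slightly wider at early times, and patients included late will have a shorter common window than 6 months from inclusion would give them.

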3.2. Secondary objectives

- To evaluate the mortality associated with COVID-19 infection in the population with genitourinary tumors. Percentage of patients alive/dead at discharge.
- To evaluate the rate (percentage) of complications that have required hospital admission and/or ICU treatment.
- Describe the frequency of asymptomatic or minimally symptomatic COVID-19 infections. Percentage of asymptomatic patients or with mild symptoms included in the study.
- Evolution of the oncological disease. Impact/influence of COVID-19 infection on the effectiveness of oncological treatment. Data will be collected on delays/modifications in follow-up or oncological treatment regimens. The average delay time and the number of modifications will be evaluated. Likewise, it is expected to obtain data on time to progression and overall survival of cancer patients, which can be compared with the reference values for each type of tumor pathology.

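### No tumour-assessment date is collected, so time to progression will look too long if patients still in contact but not re-assessed are closed at last contact

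*Combined protocol and SAP*

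**What the plan says.** The last objective in section 3.2 asks how COVID-19 affects the effectiveness of cancer treatment. It states "Data will be collected on delays/modifications in follow-up or oncological treatment regimens" and then that "it is expected to obtain data on time to progression and overall survival of cancer patients, which can be compared with the reference values", tumour by tumour.

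The fields meant to support this are in section 5.1, under "Prospective follow-up data (6 months from patient inclusion". They are the date treatment starts or restarts, a negative test beforehand, change or suspension of treatment, surgery date in neoadjuvant patients, recurrence of COVID-19, "Best answer obtained" (best response, without a date), "Date of progression to oncological treatment", "Current status" and "Last contact date". No date, method or interval of tumour assessment is listed. The only imaging item in section 5.1, "Radiological examination at the moment of greatest severity", belongs to the COVID-19 data. No field records a delay in follow-up, as distinct from a delay in treatment.

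Elsewhere:
- Section 4.1 leaves all assessments to usual practice.
- Section 4.4 declares patients who miss visits lost to follow-up, without a closing date.
- Section 4.5 names Kaplan-Meier and log-rank, without a censoring rule or a definition of progression.

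**The concern.** Progression is dated only when someone looks for it, whether by imaging, marker or clinical evaluation. Here the exposure under study may itself change when anyone looks. A patient seen or telephoned at month 6 but not assessed since the infection has no progression date and a late last-contact date. In the listed date fields that patient looks the same as one assessed at month 6 and found progression-free.

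If such records are closed at last contact, unobserved time is counted as progression-free time. Disruption of follow-up could then be read as absence of harm, and a real adverse effect of COVID-19 on tumour control could be masked. The comparison with reference values is the most exposed, because those values come from series with their own assessment timing and this study could not show its own.

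**Working it through.** The plan gives no figure to reproduce: no median, assessment interval or re-assessment rate. I checked every item in section 5.1 for an assessment date and found none. The rest is illustration.

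**Inputs.** From the documents: a 6-month window. Assumed: exponential progression with a 9-month median, so F(t) = 1 − 0.5^(t/9); 20% or 30% never re-assessed; assessments every 3 or 6 months with a random starting phase; everyone in contact to month 6 and closed there if no progression is recorded.

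**True progression by month 6.** F(6) = 1 − 0.5^(6/9) = 37.0%.

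**Share q never re-assessed, none of their progressions otherwise recorded.** Recorded = F(6) × (1 − q).
- q = 20%: 37.0% × 0.8 = 29.6%.
- q = 30%: 37.0% × 0.7 = 25.9%.

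**Stretched intervals, everyone assessed.** With interval d and random phase, recorded progression by month 6 is the average of F over the last d months. With λ = ln 2 / 9 = 0.0770:
- d = 3: 1 − (0.7937 − 0.6300)/(0.0770 × 3) = 29.1%.
- d = 6: 1 − (1 − 0.6300)/(0.0770 × 6) = 19.9% (simulation with 400,000 draws: 20.0%).

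Regular 3-monthly assessment already records 29%, not 37%, because detection lags the event. The effect of stretching from 3- to 6-monthly is therefore 29% to 20%. With a 6-month median the same change is 40.2% to 27.9%.

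**What could be masked.** With a 6-month median and q = 20%, recorded progression equals the undisturbed 50% when the re-assessed patients truly reach 0.50/0.80 = 62.5%. That is a hazard ratio of ln(0.375)/ln(0.5) = 1.42, hidden entirely.

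**Does closing at the last assessment cure it?** Only in part.
- Never re-assessed, unrelated to progression: yes. Simulated 6-month progression-free shares were 0.502 (q = 20%) and 0.499 (q = 30%) against a true 0.500 (6-month median).
- Stretched intervals: no. With a 9-month median and 6-monthly assessment, Kaplan-Meier closed at last assessment gave 46.1% progression against a true 34.5% at month 5.5, and 69.4% against 36.5% at month 5.9. As a check, each patient has one assessment at a time u uniform on 0 to 6, so the estimate at x is 1 − exp(−∫₀ˣ F(u)/(6 − u) du), which is 46.0% and 69.6%. Non-progressors leave the risk set at their only assessment, and the few who remain carry the late events.

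That rule alone would replace a favourable bias with an unfavourable one.

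**The case against.** The strongest reply has five parts.

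1. *No rule says to close at last contact.* Correct; it is inferred from the fields listed. But without assessment dates no better rule can be applied later from the study database.
2. *Patients who miss visits are lost to follow-up (section 4.4).* This stands and limits the claim. If those records close at the loss and the loss is unrelated to progression, they add no bias. It does not help with patients who remain in contact but are not re-assessed.
3. *Best response sits in the follow-up block and might have a not-evaluated category.* Possible, since its categories are not given. It could then flag patients never assessed. Being undated, it would not show when the others were assessed.
4. *Progression need not be radiological.* This also stands. The population includes prostate and germ-cell tumours, and a marker or clinical progression can be recorded without a scan. The 30% and 26% figures are therefore a worst case for each assumed share.
5. *The study is descriptive and the comparison optional.* Section 6.1 calls it descriptive, and section 3.2 says only that the data can be compared. This lowers the stakes, but assessment timing matters most in an external comparison.

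A reader might go further and infer that the more COVID-19 disrupts follow-up, the better time to progression must look, or that unassessed and progression-free patients can never be told apart. The documents support neither: the first fails where disruption also ends contact, and the second depends on best-response categories that are not shown.

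**Conclusion.** The gap is real and worth closing. As listed, the fields give no assured way to separate patients in contact but not re-assessed from patients known to be progression-free, and no way to describe assessment timing, although the objective expects follow-up to be delayed. If records are closed at last contact, the bias in these patients is towards longer time to progression.

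Its size is unknown. Under the assumed 9-month median it is about 7 points of 6-month progression with 20% never re-assessed (37.0 − 29.6), 11 points with 30% (37.0 − 25.9), and 9 points if intervals stretch from 3 to 6 months (29.1 − 19.9). These rest on exponential progression, contact maintained to month 6 and, for the first two, no progression recorded without a formal assessment. A true harmful effect of COVID-19 would act in the opposite direction and could be offset, so the observed result could fall either side of the reference value.

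This affects one part of one secondary objective. Time origin and definition of progression are also unstated, so assessment dates alone would not make the comparison interpretable.

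**What to change.** **Data.** Add to section 5.1 the date and method (imaging, marker or clinical) of the last tumour assessment before infection and of the assessments during the 6-month follow-up: at least the first, the last, and the last one before progression. These come from charts already being abstracted and need no added procedure. They would also supply the information on follow-up delays that section 3.2 promises.

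**Reporting.** Give the percentage never re-assessed and the distribution of assessment intervals.

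**Analysis.** Treat progression as interval-censored between the last progression-free assessment and the recorded progression date. Patients never re-assessed contribute no progression-free time after their last assessment. Show Kaplan-Meier closed at last contact as a sensitivity analysis. Do not rely on Kaplan-Meier closed at last assessment alone, because it overstates progression late in a 6-month window.

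**Comparison.** Give any comparison with reference values only beside the assessment timing.

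**Cost.** A few extra eCRF dates, slightly more analysis work, and wider intervals that reflect what was observed.
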